8.1.1.2. Key Secondary Endpoint

The key secondary efficacy endpoint is the mean diurnal IOP in the study eye at Month 3. The following null (versus alternative) hypothesis will be tested:

$$H_{0S}: \mu_{TM} - \mu_{CM} > \Delta \quad \text{vs.} \quad H_{AS}: \mu_{TM} - \mu_{CM} \leq \Delta$$

where μ_{TM} and μ_{CM} denote the mean diurnal IOP at Month 3 of the DE-126 and Timolol arm, respectively, and Δ denotes the noninferiority margin of 1.5 mmHg. The primary analysis of this key secondary efficacy endpoint will be performed using a MMRM based on the FAS. The model will include treatment, analysis visit (Week 2, Week 6, or Month 3), and treatment-by-visit interaction as fixed effects, and baseline mean diurnal IOP as a covariate. Correlations of mean diurnal IOPs within-subject will be modeled using an unstructured covariance matrix. The mathematical model is analogous to the model in the primary efficacy endpoint.

If there are convergence issues, covariance matrix structures other than unstructured will be tried in the following order: (1) heterogeneous Toeplitz (TOEPH), (2) heterogeneous autoregressive of order 1 (ARH(1)), (3) heterogeneous compound symmetry (CSH), and (4) compound symmetry (CS). The first covariance structure that converges will be used as the primary analysis. Least squares mean diurnal IOP values at Month 3 for each treatment arm and the difference between least squares treatment group means and its 95% confidence interval will be reported.

Noninferiority of DE-126 to Timolol is achieved for this endpoint if the upper limit of the 95% confidence interval for the difference between DE-126 and Timolol (DE 126 minus Timolol) in the mean diurnal IOP at Month 3 is ≤ 1.5 mmHg. Superiority of DE-126 to Timolol is achieved for this endpoint if the upper limit of the 95% confidence interval is < 0 mmHg.

8.1.2. Sensitivity Analyses

For the primary endpoint and the key secondary endpoints, sensitivity analyses will be performed to assess the robustness of the results from the primary analysis. The following sensitivity analyses will be performed:

- Using the analysis population of the PPS
- Using a pattern-mixture model (PMM) with delta-adjustment approach where missing values are imputed by multiple imputation.

To assess the sensitivity to departure from MAR assumption, a PMM with delta-adjustment will be applied, as follows:

- a. Use Markov chain Monte Carlo (MCMC) to create monotone missingness first. Then obtain standard multiple imputations under MAR assumptions for missing IOP values using monotone regression. The missing data are filled in and 50 complete datasets are created. The seed that will be used in the SAS program is 13546.
- b. For each IOP value that had been missing because of censoring after having received IOP-lowering rescue therapy, or early study discontinuation due to lack of efficacy or AE, these values will adjust by adding delta to the imputed values, where delta = 1.0 mmHg. The seed that will be used in the SAS program is 13546.
- c. Each of the 50 complete datasets will then be analyzed separately using the same MMRM as used for the primary analysis.
- d. The estimates obtained from the MMRM analysis of each complete dataset are combined for inference purposes.
- e. Repeat step b, c, d, with delta = 2.0, 3.0, 4.0, and 5.0 mmHg. The larger the value of delta that is required to reverse the conclusion of the primary analysis, the more robust the conclusion is considered to be.

For the primary endpoint, in addition to the two types of sensitivity analyses described above, if the overall rate of study drug discontinuation due to lack of efficacy or AE is greater than 10% and the difference between the rate in the DE-126 and Timolol arms is greater than 5 percentage points, a trimmed mean analysis ([Permutt et al., 2017](#)) will be conducted as a sensitivity analysis.

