7.1. Subject Early Discontinuation/Withdrawal from the Study

An early termination occurs when a subject who provides written informed consent ceases participation in the study, regardless of circumstances, before the completion of the study. Subjects may be voluntarily discontinued from study medication or withdrawn from the study at any time for any reason. In addition, the Principal Investigator or Medical Monitor or designee may discontinue the study drug administration or terminate a subject's study participation due to any of the following reasons:

- AE (e.g., not compatible with study continuation)
- Non-compliance with study drug
- Lack of efficacy (e.g., IOP exceeds 34 mmHg in either eye after randomization)
- Progressive disease
- Protocol deviation (e.g., not fulfilling eligibility criteria)
- Pregnancy
- Voluntary withdrawal by subject at any time for any reason
- Lost to follow-up (e.g., no contact is possible)
- Death
- Other

If the study drug administration is discontinued prior to Visit 5, they should be encouraged to still participate in all follow-up study visits until Visit 5 on an observational basis.

If the study drug administration is discontinued prior to Visit 5, then to the extent possible, all procedures for Early Termination will be performed on the day of early drug discontinuation as per [Table 3](#). Subjects who are discontinued from the study early will not be replaced.

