3.3. Sample Size Planning

The sample size calculation was based on a two-sided Type I error rate of 5% and a non-inferiority margin of 1.5 mmHg. Assuming a between-treatment difference of 0 mmHg, SD of 4.0 mmHg and a correlation coefficient of 0.6 among repeated measures, approximately 280 adult subjects in total (140 subjects per treatment arm) will provide 70% power to demonstrate non-inferiority of DE-126 Ophthalmic Solution 0.002% to Timolol maleate ophthalmic solution 0.5%. Assuming a drop-out rate of 5%, the final needed sample size will be 294 in total, i.e. 147 subjects/arm.

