8.1. Analyses of Primary Endpoint and Key Secondary Endpoint

8.1.1. Primary Analysis

8.1.1.1. Primary Endpoint

The primary efficacy endpoint is the IOP in the study eye at each scheduled timepoint (08:00, 10:00, and 16:00) at each of three follow-up visits, Week 2, Week 6, and Month 3. The nine combinations of three scheduled timepoints at each of three visits are referred to subsequently as nine timepoints. For the primary endpoint, the following hypotheses will be tested:

$$H_0: \mu_T - \mu_C > \Delta \text{ for at least one timepoint}$$

versus

$$H_A: \mu_T - \mu_C \leq \Delta \text{ at all nine timepoints}$$

where μ_T and μ_C denote the mean values of the primary endpoint in the DE-126 arm and the Timolol arm, respectively, and Δ denotes the noninferiority margin of 1.5 mmHg.

The primary analysis of the primary efficacy endpoint will be performed using a MMRM based on the FAS. A separate MMRM will be used for IOP at each scheduled timepoint (8:00, 10:00, or 16:00). For each scheduled k th timepoint, the model will include treatment (T_i), analysis visit (V_j), and treatment-by-visit interaction (TV_{ij}) as fixed effects, and the baseline IOP (B_k) as covariates:

$$IOP_{ijkn} = \mu + T_i + V_j + TV_{ij} + B_k + \varepsilon_{ijkn}$$

where μ denotes the overall mean, and ε denotes the random error associated with the individual subject. The above model allows treatment effect and its variability to vary over study visits.

Correlations of IOP measurements within-subject will be modeled using an unstructured covariance matrix. If there are convergence issues, covariance matrix structures other than unstructured will be tried in the following order: (1) heterogeneous Toeplitz (TOEPH), (2) heterogeneous autoregressive of order 1 (ARH(1)), (3) heterogeneous compound symmetry (CSH), and (4) compound symmetry (CS). The first covariance structure that converges will be used as the primary analysis. Least squares mean IOP values for each treatment arm and differences between least squares treatment arm means and associated 95% confidence intervals will be reported for each of the nine timepoints.

For the subjects who receive IOP-lowering rescue therapy, any IOP values collected after the receipt of rescue therapy will be censored (i.e., treated as missing) in the analyses.

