Noninferiority criteria for primary endpoint: With respect to the primary study objective, noninferiority of DE-126 to Timolol is established if the upper limit of the two-sided 95% confidence interval for the difference in the mean IOP (DE-126 minus Timolol) is ≤ 1.5 mmHg at all nine timepoints and ≤ 1.0 mmHg in majority (five or more) of the nine timepoints.

Superiority of DE-126 to Timolol for the primary efficacy endpoint will be claimed if the upper limit of the two-sided 95% confidence interval for the difference in the mean IOP (DE-126 minus Timolol) is < 0 mmHg at all nine timepoints.

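### The delta-adjusted sensitivity analysis uses one delta in both arms, so it barely tests non-inferiority unless adjusted values are more frequent on DE-126

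*SAP*

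**What the plan says.** SAP 8.1.2 plans a pattern-mixture analysis for the primary and key secondary endpoints. Missing IOP is first imputed under MAR (50 data sets). Step b then selects values by the reason they are missing. It opens "For each IOP value that had been missing because of censoring after having received IOP-lowering rescue therapy" and goes on to values lost when a subject leaves the study early for lack of efficacy or an adverse event. For these, "these values will adjust by adding delta to the imputed values, where delta = 1.0 mmHg". Step e repeats the run with 2.0, 3.0, 4.0 and 5.0 mmHg. No arm is named and each run has a single delta, so the plain reading is that both arms are adjusted equally. Values missing for other reasons keep their MAR imputation.

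Step e also says how to read the result: "The larger the value of delta that is required to reverse the conclusion of the primary analysis, the more robust the conclusion is considered".

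Two other sensitivity analyses are listed. One repeats the analysis on the per-protocol set. The other is a trimmed mean, for the primary endpoint only, run only if discontinuation of study drug for lack of efficacy or adverse events exceeds 10% overall and differs between arms by more than 5 percentage points. Protocol 9.5 says only that a pattern-mixture approach may be used and gives no rule by arm.

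**The concern.** In a non-inferiority trial, the missing-data departure that most directly threatens the claim is one in which missing values on the test drug are worse than MAR predicts while those on the control are not. A delta added to both arms cancels in the treatment difference to the extent that the arms have equal shares of adjusted values. Under balance, a large reversing delta, or none reached by 5 mmHg, mostly reflects that cancellation. If timolol has more adjusted values, raising delta makes non-inferiority easier, so the step e reading points the wrong way.

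Nothing else in the plan fills the gap. The per-protocol run changes the population but not the missing-data assumption. The trimmed mean requires an imbalance before it runs and does not cover the key secondary endpoint. The common-delta analysis is therefore the only check on departures from MAR that always runs for both endpoints. A statement that the result is robust to missing data could rest on an analysis that hardly moved the difference, or moved it towards DE-126.

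**Working it through.** **The plan's own figure.** The delta analysis has no stated operating characteristic. The nearest figure is the 70% power in SAP 3.3 (140 per arm, SD 4.0, correlation 0.6, true difference 0, margin 1.5 mmHg). On those inputs, one timepoint gives 88%, all nine upper limits ≤ 1.5 mmHg gives 61%, and the full rule gives 51%. The 70% is not reproduced, and the SAP does not say how the calculation treated the nine timepoints, the 1.0 mmHg condition or the baseline covariate. The present point does not depend on it.

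**Inputs.** From the SAP: SD 4.0, correlation 0.6, true difference 0 and 147 per arm (3.3); delta 1 to 5 mmHg (8.1.2); and the rule in 8.1.1.1, an upper 95% limit ≤ 1.5 mmHg at all nine timepoints and ≤ 1.0 "mmHg in majority (five or more) of the nine timepoints". Assumed: the adjusted shares pT (DE-126) and pC (timolol). The documents give only 5% overall drop-out, with no split by arm or reason.

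**Shift in DE-126 minus timolol.**
- As written: delta × (pT − pC).
- DE-126 only: delta × pT.

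At delta 5 and 5%/5%, these are 5 × (0.05 − 0.05) = 0.00 and 5 × 0.05 = 0.25 mmHg. At delta 1 the DE-126-only shift is 0.05 mmHg.

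**Interval width.** Ignoring imputation variance, the arm variance becomes 16 + delta² × p(1 − p).
- No delta: 1.96 × √(2 × 16/147) = 0.914 mmHg.
- Common delta 5 at 5%/5%: variance 16 + 25 × 0.0475 = 17.19, half-width 0.948.
- Common delta 5 at 10%/10%: half-width 0.977.

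Under balance, the common delta acts through this slight widening and through chance differences in the realised shares.

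**Share of non-inferior results reversed, delta 5** (as written vs DE-126 only; shares are DE-126/timolol):

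| Adjusted shares | Shift, mmHg | One timepoint, 1.5 limit | Nine-timepoint rule |
|---|---|---|---|
| 2%/2% | 0.00 vs +0.10 | 2% vs 6% | 5% vs 11% |
| 5%/5% | 0.00 vs +0.25 | 4% vs 16% | 8% vs 29% |
| 6%/3% | +0.15 vs +0.30 | 11% vs 21% | 21% vs 35% |
| 3%/6% | −0.15 vs +0.15 | under 1% vs 9% | 2% vs 20% |

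The one-timepoint column uses 20,000 trials per setting with randomly flagged values. At a 1.0 mmHg limit and 5%/5% it gives about 10% vs 39%. The nine-timepoint column uses 2,500 trials per setting, monotone drop-out (half of p lost before Week 6, the rest before Month 3), conditional-normal MAR imputation within arm, 8 imputations combined by Rubin's rules, and no baseline covariate.

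In the nine-timepoint simulation the chance of non-inferiority before any delta is 0.53 to 0.54.
- 5%/5%: it falls to 0.50 as written and to 0.38 with delta on DE-126 only.
- 3%/6%: it rises from 0.53 to 0.57 as written, with 11% of failed results becoming non-inferior. It falls to 0.42 with delta on DE-126 only.
- 5%/5% at delta 1: 1% vs 5% of non-inferior results are reversed.

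Repeat runs agreed within simulation error: 8% vs 29% at 5%/5%; 1% vs 17% to 18% at 3%/6%, with 13% to 14% of failures converted.

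**Baseline adjustment.** If the 0.6 correlation also holds with baseline, the residual SD is 4 × √(1 − 0.36) = 3.2. At 5%/5% and delta 5, the contrast is then 7% vs 25%, or 6% vs 21% when imputation variance is ignored.

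**The case against.** The strongest defence is that step b ties delta to the reason a value is missing, not to the arm. If subjects who need rescue or stop for lack of efficacy do worse than MAR predicts, that should hold in either arm. A shift towards DE-126 when timolol has more such subjects is then what the premise implies. The DE-126-only scenario is a deliberate worst case, and nothing in the documents says it is likely. This stands as a reason to keep the common-delta run, but not as a reason to have no other. Where pT exceeds pC, the method does penalise DE-126 and the step e reading works; the plan cannot know in advance which case will arise.

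The size can also be challenged. A 5% share treats every planned drop-out as adjusted, although step b leaves out other reasons. Under Protocol 7.1, subjects who stop drug early are told "they should be encouraged to still participate in all follow-up study visits until Visit 5 on an observational basis", and Protocol 9.7 censors post-discontinuation IOP only when other IOP-lowering treatment is used, so some of these values may be observed. Against that, SAP 8.1.1.1 says "any IOP values collected after the receipt of rescue therapy will be censored", which can raise the share above drop-out alone. Delta 5 is the top of the plan's range, and effects at delta 1 are small. Baseline adjustment trims the 5%/5% contrast without removing it.

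Finally, the analysis enters neither the non-inferiority criteria nor the fixed testing sequence, so no formal claim or error rate changes. That is correct and limits the weight of the point.

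**Conclusion.** The concern holds. As written, the delta analysis moves the treatment difference only through an imbalance in adjusted values, and the robustness reading in step e is unreliable when shares are balanced or heavier on timolol. The algebra is certain, given the plain reading that no arm restriction applies. The practical size depends on assumed shares: at delta 5, the reversal rate under the nine-timepoint rule is 5% vs 11% at 2% per arm and 8% vs 29% at 5% per arm, somewhat less after baseline adjustment. The simulations approximate the planned MMRM and do not replicate it. This should be changed before unmasking, but it affects a supportive robustness statement and not the non-inferiority decision.

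**What to change.** Keep the common-delta run. In SAP 8.1.2, steps b and e, add a run with delta applied to DE-126 values only, or a two-way grid of arm-specific deltas, for the primary and key secondary endpoints. Report the smallest delta at which non-inferiority fails. For the primary endpoint, failure means an upper limit above 1.5 mmHg at any of the nine timepoints, or fewer than five limits at or below 1.0 mmHg. For the key secondary, it means an upper limit above 1.5 mmHg. Base the robustness statement on this run, shown beside the common-delta result, and tabulate the number of adjusted values by arm and reason.

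The cost is one or two sentences in the SAP, a little more analysis work and a more conservative robustness statement. No new data are needed and the primary analysis is unchanged.

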8.2. Analyses of Other Secondary Endpoints

For continuous secondary endpoints (IOP, mean diurnal IOP, change and percent change from baseline in IOP/mean diurnal IOP) at Week 2, Week 6 and Month 3, both MMRM and descriptive summaries will be performed. The MMRM will be the same as the one for key secondary endpoint but without multiplicity adjustment.

8.2.1. Responder Rates

For binary secondary endpoints, the responder rates will be summarized at each post-baseline visit. Subjects discontinued study by any reason without response will be treated as non-responder. A sensitivity analysis will be conducted by multiple imputing for discontinued subjects with reasons other than AE or lack of efficacy. DE-126/Vehicle arm will be compared with Timolol Maleate arm using Fisher's exact test, and the differences between the two treatment arms will be reported along with 95% CIs.

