9.7. Efficacy Analyses

Unless specified otherwise, for subjects who discontinue from the study medication per protocol before the Study Exit, the IOP data collected after the study medication discontinuation with any use of non-study IOP lowering medication or surgery will be censored from all efficacy analyses.

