4.2.2. Efficacy Measure

IOP (in mmHg) is the efficacy measure for this study. For the IOP at each timepoint of measurement, a mean of two consecutive measurements using the Goldmann applanation tonometer will be used. If the two measurements differ by 3 mmHg or more, then a third measurement will be made, and the median of the three consecutive measurements will be used.

The mean diurnal IOP at each visit is defined as the mean of the three scheduled timepoints 8:00, 10:00, and 16:00 at the visit. If there are one or more missing IOP measurement at timepoints, the mean diurnal IOP will not be calculated.

To assess the efficacy of DE-126, the mean/median IOP at each scheduled timepoint (8:00, 10:00, 16:00) and the mean diurnal IOP in the study eye will be analyzed. In addition, changes and percent changes from baseline in IOP at each timepoint and the mean diurnal IOP in the study eye will also be analyzed.

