4.2.4. IOP Response Endpoints and Response Rate

Four IOP response endpoints shown in Table 3 will be evaluated at each post-Baseline visit of Week 2 (Visit 3), Week 6 (Visit 4), or Month 3 (Visit 5).

For a response endpoint, the response rate at a post-Baseline visit is calculated as the proportion of subjects who met the response criterion at the visit.

Table 3 Response Endpoints

Response Endpoint	Response criteria in mean diurnal IOP
IOP 20% response	Percent reduction from Baseline \geq 20%
IOP 25% response	Percent reduction from Baseline \geq 25%
IOP 30% response	Percent reduction from Baseline \geq 30%
IOP \leq 18 mmHg response	Mean diurnal IOP \leq 18 mmHg

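### The responder rule in SAP 8.2.1 gives no status to subjects who are rescued but stay in the study; on the more natural, observed-case reading these failures leave the response rate

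*SAP*

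**What the plan says.** The responder endpoints are reductions of at least 20%, 25% or 30% in mean diurnal IOP, and a mean diurnal IOP of 18 mmHg or less, each assessed at Week 2, Week 6 and Month 3. Five provisions decide how a rescued subject is handled.

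- **Definition of the rate (SAP 4.2.4):** "the response rate at a post-Baseline visit is calculated as the proportion of subjects who met the response criterion at the visit". The denominator is not specified.
- **Non-response rule (SAP 8.2.1):** "Subjects discontinued study by any reason without response will be treated as non-responder". The accompanying sensitivity analysis is limited in the same way: "A sensitivity analysis will be conducted by multiple imputing for discontinued subjects with reasons other than AE or lack of efficacy".
- **Staying after drug is stopped (Protocol 7.1):** for subjects who stop study drug before Visit 5, "they should be encouraged to still participate in all follow-up study visits until Visit 5 on an observational basis".
- **Censoring after rescue:** under the primary endpoint, SAP 8.1.1.1 says that "any IOP values collected after the receipt of rescue therapy will be censored (i.e., treated as missing) in the analyses". Protocol 9.7 applies censoring to every efficacy analysis: for subjects off study medication, IOP data collected after stopping with "any use of non-study IOP lowering medication or surgery will be censored from all efficacy analyses".
- **Incomplete readings (SAP 4.2.2):** "If there are one or more missing IOP measurement at timepoints, the mean diurnal IOP will not be calculated".

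Protocol 9.5 makes observed cases the default for descriptive summaries unless something else is specified.

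**The concern.** Needing other IOP-lowering treatment because the assigned drug was not enough is a plain treatment failure on an endpoint that asks whether IOP came down. Under these provisions its classification depends on something unrelated to the drug: whether the subject agrees to go on attending visits. A subject who leaves is a failure. A subject with the same course who stays has no value and no rule.

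If subjects without a value are left out of the rate, each arm's rate rises with its share of retained rescues, and the arm with more of them gains more. The responder analyses answer a stated secondary objective and are reported with Fisher's exact test and 95% confidence intervals, so the rule should be settled before unmasking.

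**Working it through.** **Step 1. Follow one subject through the text.** Suppose a subject stops drug for lack of efficacy after the Week 2 visit, starts other IOP-lowering treatment, and attends Week 6 and Month 3.

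1. Protocol 7.1 keeps the subject in the study.
2. Protocol 9.7 censors the Week 6 and Month 3 IOP from all efficacy analyses.
3. With the readings missing, SAP 4.2.2 gives no mean diurnal IOP at either visit.
4. SAP 8.2.1 does not apply, because the subject has not discontinued the study. Its multiple-imputation analysis does not apply either, for the same reason.

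**Step 2. Is the retained, rescued subject a category the SAP recognises?** Yes. In the delta-adjusted imputation of SAP 8.1.2, step b lists values censored after rescue separately from values missing through early study discontinuation. That section also uses study drug discontinuation as a distinct term, in the trigger for the trimmed-mean analysis. These subjects are therefore handled explicitly for the primary and key secondary endpoints, but not for the responder endpoints.

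**Step 3. Size on the observed-case reading.** The plan states no responder or rescue rate, so there is no figure of its own to reproduce.

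- p = response rate over all FAS subjects, with every rescued subject a non-responder (assumed 40% to 60%).
- f = share of the arm rescued, retained and censored (assumed 2% to 15%).
- n = 140 evaluable subjects per arm (SAP 3.3). A share of 5% is then 0.05 × 140 = 7 subjects.

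The dropped subjects are all non-responders, so the numerator is unchanged and the denominator shrinks:

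reported rate = p / (1 − f)

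| f | multiplier 1/(1 − f) | reported rate when p = 60% |
|---|---|---|
| 2% | 1.02 | 0.60/0.98 = 61.2% |
| 5% | 1.05 | 0.60/0.95 = 63.2% |
| 10% | 1.11 | 0.60/0.90 = 66.7% |

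**Step 4. Between-arm difference when the true rates are equal** (a correct analysis shows 0):

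| f, arm A vs arm B | reported rates at p = 50% | false advantage of A at p = 50% | range over p = 40% to 60% |
|---|---|---|---|
| 5% vs 5% | 52.6% vs 52.6% | 0 | 0 |
| 5% vs 2% | 52.6% vs 51.0% | 1.6 points | 1.3 to 1.9 |
| 10% vs 5% | 55.6% vs 52.6% | 2.9 points | 2.3 to 3.5 |
| 15% vs 5% | 58.8% vs 52.6% | 6.2 points | 5.0 to 7.4 |

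At 140 per arm none of these reaches p < 0.05 by Fisher's exact test; the smallest p-value is 0.23.

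When the shares are equal but the true rates differ, the difference is only rescaled by 1/(1 − f). For example, a true −8.0 points at f = 5% becomes −8.0/0.95 = −8.4.

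**The case against.** The strongest reply is that the documents never say rescued subjects leave the denominator. SAP 4.2.4 speaks of a proportion of subjects without limiting it to those with a value, and SAP 5 and 8 make the FAS the efficacy population by default. On a full FAS denominator, a censored subject has not met the criterion, counts as a non-responder, and nothing is inflated. The observed-case default in Protocol 9.5 is written for descriptive summaries, whereas SAP 8.2.1 also makes a formal comparison.

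This stands in part: exclusion is an inference. It is still the more natural reading. If every subject without a value were already a failure, a separate rule making study discontinuers non-responders would add little. That argument is not conclusive, because the rule also sets the reference for the sensitivity analysis that follows it. On either reading the denominator has to be stated.

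The group may also be small. Protocol 6.3.1 prohibits other IOP-lowering eye drops and no on-study rescue pathway is described. Early Termination procedures are due, where possible, on the day drug is stopped, and the visit list in Protocol 8.1.6 includes exiting the subject. Anyone handled that way is a study discontinuer and is covered. A complete pre-rescue Early Termination measurement from Day 62 on would also map to Month 3 under SAP 4.1.6. This limits the size of the gap but does not close it, because Protocol 7.1 expressly encourages continued attendance.

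Reading study discontinuation in SAP 8.2.1 as drug discontinuation would remove the problem, but SAP 8.1.2 uses the two terms separately.

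**Conclusion.** The point holds as a gap in the responder rule. A failing subject who stays has no assigned status, while the same subject who leaves is a failure. On the observed-case reading an arm's rate is multiplied by about 1.02 if 2% are rescued and retained, and by about 1.05 if 5% are. Both shares are assumptions.

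A reader might infer more, and the documents do not support it:

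- **That the SAP states that rescued subjects are excluded.** It leaves the denominator open.
- **That the arm with more treatment failures is necessarily favoured.** What matters is the share rescued and also retained. Both arms are inflated, and a false difference between equal true rates needs unequal shares, which the documents do not give.
- **That the distortion is large.** Differences of 5 points or more in the tables need 15% against 5% retained rescue, while the sample size assumes 5% drop-out.
- **That a confirmatory claim is at risk.** These are other secondary endpoints outside the fixed sequence in SAP 6.4, and the delta-adjusted sensitivity analysis covers post-rescue values for the primary and key secondary endpoints.

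This should be corrected before unmasking, but it does not threaten the trial's main conclusion.

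**What to change.** Amend SAP 8.2.1 to state that:

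1. The denominator at each visit is all FAS subjects.
2. A subject whose study-eye IOP at that visit is censored because of IOP-lowering rescue medication or surgery is a non-responder at that visit.
3. A subject who discontinued the study without a valid response mapped to that visit is a non-responder. The existing without-response qualifier should stay; otherwise a subject who exits after Day 62 with a valid responding Month 3 measurement would be turned into a failure.
4. On-study subjects missing a mean diurnal IOP for other reasons, such as one missed clock time, are handled by a named rule in the main analysis. One option is non-responder, with multiple imputation as the sensitivity analysis. The present imputation covers discontinued subjects only, so its scope would have to be widened explicitly.

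The text should also say which measurement governs when a pre-rescue and a censored measurement fall in the same analysis window.

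The cost is a few sentences and one programming flag, with no new data and no change to how subjects are managed. The downside is that reported response rates may be slightly less favourable.
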